**C. BACKGROUND, SIGNIFICANCE, AND RATIONALE**

Procedural Sedation and Outcomes

Pediatric emergency medicine providers administer procedural sedation to minimize patient discomfort and anxiety during diagnostic testing and therapeutic treatments (Kannikeswaran et al., 2017). Institution-specific protocols, individual patient factors, and intended procedures to be performed impact the sedative and analgesic medications administered. Despite highly skilled practitioners and guidelines emphasizing safe and methodical practice, procedural sedations carry risk for adverse effects (Cote et al., 2016). Well-established anesthesia literature of post-operative patients and increasing pediatric emergency medicine literature demonstrates that the adverse effects of anesthesia and procedural sedations are not limited to respiratory, cardiovascular, or gastrointestinal signs and symptoms. Significant and lingering negative behavioral changes can be seen weeks to months post-sedation which have implications for patients and their families that extends beyond the walls of the hospital (Hilly et al., 2015).

Several studies have documented post-operative negative behavioral changes in children following anesthesia and surgery (Eckenhoff 1953, Pearce et al., 2017, Thompson 1993). Investigations have shown that hospitalization and anesthesia can impact children psychologically and behaviorally and contribute to post-operative negative behavioral (PONB) changes (Stargatt et al., 2006, Karling et al., 2006). PONB effects include increased anxiety, sleep disturbance, nightmares, apathy, and eating difficulty (Karling et al., 2005,

Keaney et al., 2004). Children with high anxiety prior to anesthesia or emergency department (ED) procedural sedation are even more vulnerable to develop PONB changes (Beringer et al., 2014, Kain et al., 1996, Kain et al., 1999, Pearce et al., 2018, Zavras et al., 2015). In one study, “very anxious” children were found to be 40% more likely to suffer these changes (Kain et al., 1996).

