- **Procedure Measures:** Variables that might be associated with the primary outcome will be collected. Following the procedure, charts will be reviewed to collect: 1) the type of pain medication given in the ED, 2) the dose (mg/kg and total number of doses) of pain medication given in the ED, 3) the anxiolytic medication given in the ED, 4) the dose (mg/kg and total number of doses) of anxiolytic medication given in the ED, 5) the type of pain medication prescribed for home, and 6) the dose (mg/kg and total number of doses) of pain medication prescribed for home. See Appendices E and F.
- **Outcome Measures:**
  - **Post-Hospitalization Behavior Questionnaire (PHBQ):** See Appendix F. The PHBQ is a parent-report questionnaire with 27 items in six categories, comprising general anxiety, separation anxiety, sleep anxiety, eating disturbance, aggression towards authority, apathy, and withdrawal. This questionnaire has been used extensively since its development in 1966 to study negative behavioral changes in children post-surgery or hospitalization (Kain et al., 1996, Kain et al., 1999) and was recently used to evaluate the same after minor ED procedures (Brodzinski et al., 2013). This questionnaire takes approximately 10 minutes to finish. This tool will be completed by a parent(s)/guardian(s) prior to the sedation and during phone or mail follow-up post-sedation.

Procedures of the study: The study procedure is outlined in the diagram below (Figure 1).

Figure 1. Procedures of the study

Patients will be identified by trained research assistants (or other member of the research team) and enrollment criteria will be reviewed. Parent/guardian consent will be obtained for all eligible patients. A separate assent form will be completed for patient's aged 7- 13 years. Demographic information will be collected from the parent/guardian.

Patient's anxiety measures using the m-YPAS will be completed at baseline by the patient's medical provider (attending physician or fellow physician). A PHBQ will be completed at baseline by the patient's parent. Patients will then be stratified into high and low anxiety groups based on their baseline m-YPAS score (score of 40 or greater being highly anxious) (Pearce, et al., 2017, Kim, et al., 2012, Kain, et al., 2006) and randomized in blocks of 4 by a computer to either the control or experimental group on a 1:1 ratio. See Figure 1.

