The VR headset, device, and software, created by Stanford's Childhood Anxiety Reduction through Innovation and Technology (CHARIOT)program/Weightless Studio, LLC will be utilized in this study. Patients in the VR intervention group will be allowed to select a distraction-based game to play with active VR content featuring interactive avatars and interactive experiences tailored to the pediatric population that allow players to do things such as control penguins sliding down a mountain while collecting pebbles for points, control puppies running in space to collect treats to the rhythm of music, and control an asteroid miner exploring an asteroid belt and collecting points based on color of asteroids collected, for example. See appendix H.

The game will last a minimum of 5 minutes in duration, provided patient tolerance. The patient may play longer if desired prior to receiving procedural sedation and the total length of activity played will be documented by the RA who will record patient's start and stop time. The VR device will not be applied until the pending time of the procedure is known, such that it will be removed from the participant no longer than 5 minutes before the sedation procedure is initiated, provided patient tolerance. The VR device will be removed when the X-ray technician team arrives to the room prior to the start of the sedation. The time from VR removal to the time of m-YPAS assessment and time of sedation medication administration will be collected and analyzed.

The VR intervention will require the use of the patient's head to navigate the characters in the game (i.e. looking left, right, up or down) and will not require the patient to get out of bed, move their arms, or legs. The research assistant (or other member of the research team) will initiate the VR intervention for patient, record the duration of intervention, and denote any reports of distress including nausea or dizziness (See Appendix I). Parents will be asked to remain at the bedside with the patient throughout the VR intervention, keep the rails of the bed up at all times, push the call light to notify the RA when the child has completed the game, and advocate for their child if the VR experience is poorly tolerated as an additional safety measure.

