### **H. RISKS AND THE PRECAUTIONS WHICH WILL BE TAKEN TO MINIMIZE RISK EXPOSURE**

This research does not involve greater than minimal risk to children. The only risks to patients and their families are the 30-minutes required to complete the surveys, potential risk for nausea/dizziness or headache, the 5-minutes for follow-up contact (via phone call, secured REDCap email, text, or mail), and the risk of confidentiality outlined below. Patients with preexisting nausea, vomiting, dizziness, or a history of motion sickness are excluded from participation in the study. We expect a 2.5% or lower incidence of intolerability (primarily nausea and dizziness), in which case the VR headset can simply be removed and any follow up care can be assessed by the patient's medical provider (Aminabadi et al., 2012, Wismeijer and Vingerhoets, 2005, Gold et al. 2006). Treatment for the low but potential risk of dizziness and/or nausea is primarily to remove the device, as consistent with other studies. Medical providers will evaluate patient at bedside and determine if further intervention, such as an anti-emetic is indicated. The study does not cover the cost of nausea medication, should it be required. This is clearly explained in the consent/assent documentation for review prior to participation.

Per recommendations of the IRB administrative offices, VR, being implemented as a distraction tool in the form of an interactive game prior to sedation for pediatric patients in the Emergency Department, is considered a medical device. We are submitting the FDA form regarding the use of a device in a study because this is being considered a "medical device" at CHW due to the following description, "it is ...intended for use in the potential mitigation of anxiety , in man, or other animals." The use of the device is hypothesized to reduce (mitigate) post-sedation negative behavior changes and pre-sedation anxiety as measured by PHBQ and m-YPAS scores, respectively. We contend that the device while viewed this way is at least a non-significant risk (NSR) device and can be ruled on by the IRB.

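### As described, VR harm is noted only in the VR arm and tied to the VR session; no vomiting or anti-emetic data are planned in either arm, so the trial gives no between-arm estimate for VR used shortly before sedation.

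*Combined protocol and SAP*

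**What the plan says.** All references are to the combined protocol and SAP.

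- **Harm record.** In section D (Procedures of the study), the research assistant who starts the VR session is to "record the duration of intervention, and denote any reports of distress including nausea or dizziness", with a pointer to Appendix I. Only children given VR can generate this record.
- **Timing.** Section D plans that, tolerance permitting, the headset is "removed from the participant no longer than 5 minutes before the sedation procedure is initiated". It adds: "The VR device will be removed when the X-ray technician team arrives to the room prior to the start of the sedation".
- **After the headset comes off.** Section D then describes the second m-YPAS, sedation under ED policy, discharge and follow-up. None of these steps records nausea, vomiting or anti-emetic use. Follow-up is the PHBQ plus three questions on opiates.
- **Chart review.** Section D (Procedure Measures) states "Following the procedure, charts will be reviewed to collect: 1) the type of pain medication given in the ED". Five more items follow, among them "the anxiolytic medication given in the ED". The stated purpose is to gather variables that may relate to the primary outcome. Appendices E and F are cited.
- **Risk.** Section H expects intolerability, mainly nausea and dizziness, in at most 2.5% of children. It says the provider will "determine if further intervention, such as an anti-emetic is indicated", but not that this will be captured as data. Section C acknowledges that "the adverse effects of anesthesia and procedural sedations are not limited to respiratory, cardiovascular, or gastrointestinal signs and symptoms", which takes gastrointestinal effects of sedation as established.
- **Analysis and monitoring.** Section O contains no harm analysis. Section J, although headed as safety monitoring, covers study IDs and data storage. Sections L (stopping points) and M (monitoring board) read N/A.

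**The concern.** The plan places an exposure whose main expected side effect is nausea a few minutes before a drug procedure with recognised gastrointestinal effects. It then collects no outcome on the two together. The VR-session note has no comparator. Symptoms that appear once sedation has begun cannot be attributed to VR without a control arm, because sedation alone can cause them.

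Randomisation supplies that control arm, and a chart review is already planned after each procedure. What is at stake is any tolerability statement made at the end of the trial. As described, it would rest on an uncontrolled note from one arm, while section K already presents VR as safe and well tolerated.

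**Working it through.** **1. The places where harm data could arise, side by side**

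| Step (section) | VR arm | Control arm |
|---|---|---|
| VR session (D) | distress, nausea, dizziness noted | nothing |
| Headset removal to sedation (D) | times and m-YPAS | m-YPAS |
| Sedation to discharge (D) | nothing described | nothing described |
| Chart review, six items (D) | pain and anxiolytic drugs | the same |
| Follow-up at 7–14 days (D) | PHBQ, three opiate questions | the same |
| Analysis (O) | no harm analysis | no harm analysis |

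No row gives a harm variable measured in both arms.

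**2. The plan's own sample size (section E)**

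Inputs: 25% against 10%, alpha 0.05 (taken as two-sided), 80% power, 20% dropout.

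- n per arm = (1.960 + 0.842)² × (0.25×0.75 + 0.10×0.90) / 0.15² = 7.851 × 0.2775 / 0.0225 = 96.8, so 97.
- Total = 2 × 97 / 0.80 = 242.5, so 243.

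The stated figures reproduce with unpooled variance. Dropout concerns the one-week questionnaire and does not affect ED charts, so a chart-based outcome could use 243 / 2, or about 121 per arm.

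**3. What the VR-session note can give**

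- At the protocol's 2.5%, the expected number of reports is 0.025 × 121 = 3.0.
- With no reports at all, the one-sided 95% upper limit is 1 − 0.05^(1/121) = 2.45%. This bounds symptoms noted in the VR session only and says nothing about a difference from control.

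**4. What two chart fields could give**

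The documents state no control rate p for vomiting or anti-emetic use, so 5% to 20% is assumed.

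- 95% half-width = 1.96 × √(2p(1−p)/121), taking similar rates in both arms. For p = 10%: 1.96 × √(0.18/121) = 0.076.
- Power for an increase d = Φ{[d√n − 1.96√(2p̄(1−p̄))] / √(p(1−p) + (p+d)(1−p−d))}, where p̄ = p + d/2 and n = 121.

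| Assumed control rate | 95% half-width | Increase detectable with 80% power | Power for a 5-point increase |
|---|---|---|---|
| 5% | 5.5 points | about 11 points | 31% |
| 10% | 7.6 points | about 13 points | 22% |
| 15% | 9.0 points | about 15 points | 17% |
| 20% | 10.1 points | about 16 points | 15% |

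If charts were used only for the 97 per arm with follow-up, the half-widths would be 6.1, 8.4, 10.0 and 11.3 points.

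**The case against.** The strongest case against has five parts.

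- **No stop time is written.** A reader might infer that harm recording ends before ketamine is given. The documents do not say so. They tie the note to the VR session and describe no later recording. Study contact does continue, because the time from removal to m-YPAS and to sedation medication is collected. The supportable statement is that no later recording is described.
- **Forms not seen.** Appendices E, F and I may hold more fields. This stands as a limit. The explicit six-item list is still good evidence of what the chart review is meant to collect.
- **Limited yield.** A reader might infer that the extra fields would settle the safety question. They would not. Half-widths of 5.5 to 10.1 points are about two to four times the 2.5% that section H expects, and power for a 5-point increase is 15% to 31%. This stands, and it is why a descriptive estimate is proposed and not a test.
- **Harm would not vanish.** A reader might infer that more vomiting would go unnoticed. Section H has providers assess VR nausea at the bedside, and sedation follows ED policy. Events documented in care would be in the chart and could be abstracted later through the link file in section J. The gap is in planned study data. The N/A entries in sections L and M do not enlarge the point, since fields abstracted after the procedure are not monitoring.
- **Efficacy aims, minimal risk.** Both aims concern efficacy, the study is classed as minimal risk, and children with current nausea or severe motion sickness are excluded. This limits the weight of the point. It does not explain leaving the one named device risk without a comparator when charts are already being opened.

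**Conclusion.** The point holds as a gap in planned data capture and reporting. On the body text, no harm variable is measured in both arms, and the trial will give no between-arm estimate of vomiting or anti-emetic use for VR given shortly before sedation. Nothing in the documents shows that VR raises either, and that is not claimed.

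Adding the fields would move the trial from no estimate to one with a 95% half-width of about 5.5 to 10.1 points. This rests on about 121 children per arm with usable charts, on assumed control rates of 5% to 20%, and on Appendices E, F and I not already holding the fields. The change is worth making but does not bear on the validity of the primary or secondary analysis.

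**What to change.** - **Section D, Procedure Measures.** Add two yes/no items for all randomised children in both arms: (7) any anti-emetic given and (8) any vomiting. Count each from randomisation to ED departure, whether by discharge or admission. One common window keeps the arms comparable and covers the interval between headset removal and sedation.
- **Children later excluded.** Section D treats children whose admission becomes known only afterwards as screening failures. Keep them in this tabulation. Otherwise a child admitted because of vomiting would drop out of the comparison.
- **Section O.** Report both items by randomised arm, with counts, risk difference and 95% confidence interval, descriptively and without a test.
- **If the fields already exist** in Appendix E, F or I, list them in section D and add only the table.

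**Cost.** Two more fields in a review already planned and one more table. Precision is limited, charting may be incomplete, and anti-emetic use is at the discretion of providers for whom no blinding is described, so that item may partly reflect knowledge of allocation. The change concerns data capture only and alters no clinical management.

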At the closure of the game the research assistant (or other member of the research team) will remove the headset. The headset will then be thoroughly cleaned with hydrogen peroxide wipes and/or replacement of facemask according to standard infection control recommendations for the CHARIOT VR device before the next study participant's use. See Appendix J.

After intervention and immediately preceding sedation, anxiety measures using m-YPAS will be reassessed by the medical provider (attending physician or fellow physician).

The physician will perform the sedation per CHW ED sedation policy. The sedation will be administered and as appropriate the patient discharged. Child life consultation by nursing staff or medical provider as an adjunct to patient care during ED course will be permitted per standard procedure and noted. See Appendix K.

Follow-up with the family will be performed by the research assistants (or other member of the research team) between 7-14 days after ED discharge consistent the procedures followed previously (Pearce et al., 2017). Phone, secured REDCap email/text, and mail surveys will be sent. One PHBQ and pain survey will complete the study. Follow up contact via email/text will include instructions for the parent to complete the PHBQ survey and pain questions via a link that will be provided through the secured REDCap database and record their responses electronically. Script content will be consistent with the example documented in Appendix L. The phone follow-up attempts will take place during the hours agreed upon by the parent(s)/guardian(s). The phone follow-up attempts will occur no more than two times per day during the follow-up period. During the phone, email, text or mail follow-up, the PHBQ post-sedation will be administered to assess the degree of change PONB changes post-sedation as well as 3 additional questions regarding post-discharge pain treatment: (1) Was your child prescribed an opiate medication (ie. oxycodone) prescription for pain control at home? (2) Did you fill this prescription? (3) Have you given your child an opiate medication for the pain following discharge from the ED? This phone survey was utilized in a prior study and took no longer than 5 minutes to complete. If the parent(s)/guardian(s) are not reachable by phone after the period specified above, then a paper copy of the follow-up survey will be mailed to him/her along with a self-addressed stamped envelope for return of the survey.

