In anticipation of funding, a gift card in the amount of 25.00 will be provided to the child if their parent/guardian completes the study's follow up 1-week PHBQ, our primary outcome of interest. The Research Assistant will track study completion via REDCap and mail receipt of the PHBQ. The gift card will be provided within 1 week of receiving the survey results either via email or mail with the contact information provided upon study enrollment. If the parent/guardian does not complete the 1-week follow up survey, a gift card will not be sent. This incentive will be described to study participant and their parent/guardian at the time of enrollment and detailed in the assent/consent forms.

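### Staff who set up VR with a child may also take that child's primary-outcome PHBQ by phone, and the protocol neither conceals the arm from the caller nor fixes the order or number of contacts

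*Combined protocol and SAP*

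**What the plan says.** All of the relevant text is in section D (Design and Methods) of the combined protocol and SAP.

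- **VR delivery.** A research assistant or another team member explains the device, fits it and starts the game: "The research assistant (or other member of the research team) will initiate the VR intervention for patient". The same role logs duration and any distress, and removes the headset. That person knows the arm.
- **Follow-up.** The same role makes contact 7 to 14 days after discharge: "Follow-up with the family will be performed by the research assistants (or other member of the research team").
- **Modes.** "During the phone, email, text or mail follow-up, the PHBQ post-sedation will be administered". No order between phone and the electronic link is given. Calls are made at hours agreed with the parent, at most two per day.
- **Status of the outcome.** The gift-card paragraph rewards the family if the parent "completes the study's follow up 1-week PHBQ, our primary outcome of interest".
- **Partial safeguards.** Parents who use the REDCap link "record their responses electronically", with no interviewer. "Script content will be consistent with the example documented in Appendix L"; that appendix is not among the documents available for this review. If parents "are not reachable by phone after the period specified above, then a paper copy of the follow-up survey will be mailed", with a stamped return envelope.

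The design is described only as randomised, with no level of blinding. The one withholding rule is that the m-YPAS score is kept from the physician, which does not bear on the PHBQ.

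**The concern.** The primary comparison is the proportion of children with negative behavioural change, and that classification comes from the PHBQ. A caller who knows the arm, and who may have played the game with the child days earlier, could affect the result in two ways.

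1. **What is recorded.** Tone, prompting or the handling of an uncertain answer can differ by arm when the questionnaire is taken by phone.
2. **Who is reached.** The calling rule is a ceiling and not a schedule, so persistence is left to the caller. The plan expects 20% dropout, so uneven effort could make follow-up differ by arm.

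Both add to the bias already present because the parent knows the arm. Unlike that bias, both can be reduced by how follow-up is organised.

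**Working it through.** **1. The two tasks side by side.** Section D gives VR set-up and the follow-up contact to the same role. It contains no sentence that separates the two tasks for a given child or conceals the arm at follow-up. The text therefore permits the same person to do both. It does not require it.

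**2. Room for uneven persistence.** If the window of day 7 to day 14 is counted inclusively, it has 8 days. At no more than two calls per day, the ceiling is 8 × 2 = 16 calls, and no planned number is set below it. Section E gives 243 enrolled and 97 per group evaluable, so 243 − 2 × 97 = 49 children are expected to have no outcome. Who falls among those 49 can depend on calling effort.

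**3. The plan's own sample size.** Inputs from section E: 25% against 10%, significance level 0.05 (two-sided assumed), power 80%, dropout 20%. The 1:1 ratio is in section D.

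- n per arm = (p₁q₁ + p₂q₂)(z₀.₉₇₅ + z₀.₈₀)² / (p₁ − p₂)²
- = (0.1875 + 0.0900)(1.960 + 0.842)² / 0.15² = 96.8, rounded up to 97
- total = 194 / 0.80 = 242.5, rounded up to 243

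The stated figure reproduces, and nothing in this point changes it.

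**4. Size of a caller effect.** Net shift in the VR arm = (share of PHBQs completed by phone) × (bias per phone interview). The documents give neither factor. For orientation only, with an assumed 6-point bias per phone interview:

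- phone share 25%: 0.25 × 6 = 1.5 points
- phone share 50%: 0.50 × 6 = 3 points

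**5. What such a shift does to the test.** Assumptions: true rate 25% in both arms, 97 per arm, uncorrected chi-square at two-sided 0.05, all outcome pairs enumerated exactly. The table gives the probability of a significant result in favour of VR.

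| Net shift in VR arm (points) | Reported rates, control vs VR | Probability of false result favouring VR |
|---|---|---|
| 0 | 25% vs 25% | 2.5% |
| 1.5 | 25% vs 23.5% | 4.4% |
| 3 | 25% vs 22% | 7.2% |

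Shifts of 5 and 7.5 points would give 13.1% and 25.0%. With half the forms taken by phone, they would need 5 / 0.50 = 10 and 7.5 / 0.50 = 15 points of bias per phone interview. The latter equals the whole design effect of 25% − 10% = 15 points. At a 25% phone share they would need 20 and 30 points, and a 30-point reduction is impossible from a 25% rate. They are therefore not a sensible range for a caller effect. The effect of uneven persistence is not quantified here.

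**The case against.** The strongest reply is that concealing the arm from the caller gains little. The PHBQ is a parent report. Parents are told of both groups at consent, are asked to stay at the bedside during VR, and there is no sham. They know the arm whoever telephones, and some will mention it. The plan also limits the caller's role through a self-completed link, a script, a daily cap on calls and a mailed form, and none of these differs by arm.

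Most of this stands. Parent knowledge is probably the larger source of bias, and no change to follow-up would remove it. The existing measures do limit the problem, and interviewer influence can act only on forms taken by phone. What does not follow is that the remaining part should be left. A script standardises wording but does not conceal the arm, a daily cap does not equalise effort, and the link helps only families who use it.

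There is also a practical objection: recruitment already depends on staff being available, staffing numbers are not given, and calls must fit the parents' hours. A different caller for every child may not always be possible.

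Three stronger readings are tempting and are not supported:

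- **That callers will see the arm.** The documents are silent on REDCap user rights, and Appendix L cannot be checked. The text supports only that no concealment is stated.
- **That callers explain or interpret items for parents.** Section D says only that the questionnaire is administered.
- **That false-positive rates of 13% or 25% measure this problem.** They describe a shift across the whole VR arm from any cause.

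**Conclusion.** The point holds in a limited form. As written, the protocol lets staff who know the arm take the primary outcome by phone, with no stated concealment, no order of contact modes and no planned number of attempts. This is a removable addition to a bias from unblinded parents that cannot be removed. That the trial is open to parents is an inference from the bedside presence and the lack of a sham; the protocol does not use the term.

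The size of the caller effect is unknown. A rise in the one-directional error from 2.5% to about 4% to 7% is an illustration that rests on an assumed net shift of 1.5 to 3 points, a 25% rate in both arms and 97 evaluable per arm. It is not an estimate for this trial. The sample size and the primary test are unaffected. This is a low-cost improvement to the conduct of follow-up and not a flaw that undermines the design.

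**What to change.** Amend the follow-up paragraph of section D to state that:

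- the self-completed REDCap link goes first to every family, and phone is used only for non-responders;
- the planned number of contact attempts is the same in both arms, within the existing daily cap;
- the arm is hidden in the REDCap view used for follow-up;
- calls are made, from existing staff, by a team member who neither enrolled that child nor delivered VR to that child;
- the mode of completion (link, phone or mail) is recorded for each PHBQ, so that the phone share is known and results can be examined by mode.

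The existing script and mailed form stay as they are. REDCap is already the study platform, and the current wording already allows another team member to make the call. The cost is a user-rights setting, one extra data field and some scheduling effort, which may be harder when few staff are available. Some parents will still reveal the arm during a call, and the parents' own knowledge of it remains.
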